#### *Hawthorne effect*

The Hawthorne effect describes a phenomenon of an unintentional change in behavior in response to the presence of an observer. The Hawthorne effect can affect any study that involves observation of the study subjects and can therefore not be completely eliminated (12). It is known that the Hawthorne effect typically fades with time, as the subjects are getting used to the observation, especially if the presence of an observer is not directly visible. Two factors may reduce the Hawthorne effect in our study: 1) long duration of the study over 12 months, which is likely to lead to an acclimatization of the subjects once the novelty of the cameras wears off. 2) Video recordings will be made with small surveillance cameras that are mounted on the wall. The unobtrusive nature of the observation is likely going to accelerate the habituation, further reducing the Hawthorne effect.

#### *Disclosure of errors and adverse events*

Technical errors in our study are defined as the smallest measurable unit reflecting a non-deliberate action or deviation from a plan. These alone may not have the potential to lead to adverse outcome. Such errors may be the dropping the needle whilst suturing or the incorrect orientation of the needle driver, or communication that does not follow a closed loop reconfirmation. “Events” represent the next level of error analysis and these have the potential to influence outcome, if not rectified. Examples would be a serosal injury of small bowel, which would require suture repair. An event in communication representing miscommunication for example would be poor instructions leading to the opening of the wrong sterile instrument causing additional cost. In the case of patient events needing medical rectification these will naturally as per standard practice be described in the OR notes and documented. This is the standard operating procedure for these types of events. In cases with more severe consequences the intraoperative complication will be discussed with the patient as per standard of care.

Study data is abstract and at this point not linked to outcome. Only factors, which actually influence the treatment or need rectification will be discussed with the patient. This is already the standard procedure and will not be changed during the study. Incidental findings during the surgery will naturally be discussed with the patient since this is standard medical care.

#### *Sample size*

This study represents a pilot study to establish knowledge about time delay rates, surgical technical and non-technical skill components as well as to determine failures in technology (equipment failure). These numbers are currently unknown and we therefore hope to obtain an adequate knowledge base for future research in this field. What is known is that operating room cancellations and delays occur. These represent aberrations from the ideal task execution, which occur non-deliberately. They do not necessarily cause measureable effects in outcome. It is more likely, that an accumulation of events (that results from an issue that requires corrective measure) can influence a number of outcome parameters such as OR time, cost, and even patient outcome. But the delay rate itself may be influenced by other parameters such as patient factors (weight, gender, comorbidities, etc.).

### *Setting*

The study will be conducted at St. Michael's Hospital – a University of Toronto affiliated, tertiary-care teaching hospital.

### *Evaluation of collected data*

#### 1) Time delays

Data for the time period that the patient enters and exits the OR will be captured with the OR Black Box technology. Recordings will begin once the patient enters the operating room and will be stopped once she leaves. Blurring of her face and sensitive body parts will be performed by a study team member prior to data analysis. The objective time stamps and occurrence of events to be collected are outlined in Appendix 3.

#### 2) Non-Technical Skills

Video- and audio-recordings of all procedures will be evaluated by the OR Black Box data analysts with formal training in CRM-evaluation using SPLINTS(13), NOTSS (14), and/or the ANTS rating scales (Appendix 4, 5, 6). The SPLINTS and the NOTSS rating scales were derived from frameworks for the observation of team behaviors and have been modified for use in surgical teams (13-15). The ANTS framework has been developed to assess the non-technical skills of the anesthesia team. These rating scales have previously been shown to have construct validity and good inter-rater reliability. Recordings of any patients that encounter complications directly related to the index procedure will be reviewed and screened again using the SPLINTS, ANTS and the NOTSS rating scales (Appendix 4, 5, 6). Twenty percent of recorded procedures will be randomly selected for evaluation by a second observer using these tools. The second observer for the blinded evaluation of the audiovisual recordings will be a surgeon with experience in the use of behavioural rating scales. The intra-class correlation coefficient (ICC) will be determined for the results of both observers. An ICC equal or greater than 0.75 will be considered acceptable.

### *Primary Outcome Measure*

The primary objective of this study is to measure the incidence and categorization of intra-operative time delays. Secondary outcome measures will be the incidence of events leading to time delays when evaluating in retrospection, the interaction of non-technical skills and their impact on events leading to time delays, correlation of time delay to its root cause, the amount of time taken to complete a procedure, the number of canceled cases, and OR utilization (ratio of number of canceled/completed cases).

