### **III. Research Objectives**

- 1) To prospectively identify patterns or chain of events leading to prolonged case duration in total laparoscopic hysterectomy procedure in a gynecologic surgical population.
- 2) To assess how non-technical skills and team performance of surgeon, nursing and anesthesiology teams correlate with case duration and subsequent cancellations.

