#### *Data collection*

All eligible procedures will be continuously video- and audio- recorded. A panoramic view of the entire OR will be obtained using multiple surveillance cameras. The inside view of the laparoscopic camera will be recorded, as it is already standard practice. Video and audio recordings will start once the patient has entered the operating room and the user has started capture. Recordings will end when the patient exits the room and the user ends capture. The video and audio recordings will be automatically encrypted at the point of capture and stored behind a secure firewall within St. Michael's hospital. The encrypted videos will be transferred by secure socket connection to a St. Michael's Hospital research center - the International Centre for Surgical Safety (ICSS) – which is also protected by a secure firewall, where the videos will remain in a 'badge-access-only' office, on a multiple-password-protected computer. Next, a single study staff member with access to this computer will decrypt the videos and "blur" any frames in which the patient's face and/or sensitive body parts (i.e. genital area, breasts) are visible in order to preserve the patient's anonymity and dignity. The study staff member will then re-encrypt the files which will remain encrypted in the same protected environment until a certified clinical data analyst (i.e. a non-study-staff employee of ICSS who is rigorously trained to review operative videos) decrypts the videos and analyzes the videos for variables of interest as described in detail below.

Patient demographics as well as diagnoses and risk factors will be collected on an electronic patient data sheet (Appendix 2). The information on the patient data sheet is important for the study to stratify the data for patient risk factors and to identify organizational factors such as delays and environmental influences such as time of day. Video- and audio- recordings as well as all other recordings of data will capture time but not date. The time of day is important, since some factors such as vigilance can be affected

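### The event-related secondary outcomes count events only once a delay has been attributed to them in hindsight, so on their own they cannot separate events associated with delay from common background events

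*Protocol*

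**What the plan says.** Protocol, Section V, *Primary Outcome Measure*, gives the main aim: "The primary objective of this study is to measure the incidence and categorization of intra-operative time delays". Among the secondary outcomes it lists "the incidence of events leading to time delays when evaluating in retrospection", then the interaction of non-technical skills and "their impact on events leading to time delays, correlation of time delay to its root cause".

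Section III sets the aim that these outcomes serve: "To prospectively identify patterns or chain of events leading to prolonged case duration". Sections I and IV likewise look for root causes and for a chain of events behind delays.

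Data capture is wider than the outcome wording:

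- *Data collection*: "All eligible procedures will be continuously video- and audio- recorded".
- *Time delays*: "The objective time stamps and occurrence of events to be collected are outlined in Appendix 3". Appendix 3 is not in the text at hand.
- *Non-Technical Skills*: "Video- and audio-recordings of all procedures will be evaluated by the OR Black Box data analysts".

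The *Data collection* section also says that the recordings are deleted after 30 days, apart from a small sample of short segments.

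*Statistical Analysis* promises a descriptive analysis of events and outcomes, and a logistic regression on non-technical and team factors whose dependent variable is not named. Nowhere does the protocol state a comparison of event frequency by delay status.

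**The concern.** An event enters the first of these outcomes only after a delay is known and has been traced back to it. The other two carry the same condition: one concerns the effect of skills on those selected events, and the other links a delay to a cause that is assigned only where there is a delay. An event that occurred without a delay has no place in any of the three.

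This fits poorly with the rest of the protocol. The section on disclosure of errors defines events by what they could do to the outcome if left uncorrected, so events without a delay are expected. The *Sample size* section expects that events adding up may affect operating time, and examining that needs event counts in every procedure, including the smooth ones.

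The causes found are meant to feed a standardized efficiency framework (Sections IV and VII), and *Experimental Design* names a randomized sub-study of such a framework. If causes are ranked by how often they are credited with delays, frequent events of no consequence can rise in the ranking because they are frequent.

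**Working it through.** The protocol has no figure to reproduce. It gives a minimum of 60 procedures and says that a power calculation cannot be done. Delay and event rates are not given, so every rate below is an assumption, and delay is treated as yes/no per procedure.

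**Step 1. Full table for an unrelated event.** Inputs: N = 60 (*Study Subjects*), delay proportion d, event proportion e, independent of each other. The cells are N·d·e, N·d·(1−e), N·(1−d)·e and N·(1−d)·(1−e).

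| Assumed d, e | Delayed: event / none | Undelayed: event / none | Odds ratio |
|---|---|---|---|
| 0.50, 0.40 | 12 / 18 | 12 / 18 | 1 |
| 0.30, 0.20 | 3.6 / 14.4 | 8.4 / 33.6 | 1 |

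**Step 2. The same event under the outcome as worded.** Let a be the share of the events in delayed procedures that reviewers credit with the delay. The counted events are a·N·d·e in delayed procedures and 0 in undelayed ones.

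- d = 0.50, e = 0.40, a = 1: delayed 12 / 18, undelayed 0 / 30.
- d = 0.30, e = 0.20, a = 1: delayed 3.6 / 14.4, undelayed 0 / 42.

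Setting a = 1 treats presence as attribution and is the extreme case. With a = 0.5 the first line becomes 6 counted events (0.5 × 12) in delayed procedures and still 0 in undelayed ones. For any a above 0, the proportion of counted events that come with a delay is 100%, against a true 50% or 30%, and the odds ratio is infinite for an event with no effect. The zero comes from the definition and not from the data.

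**Step 3. Effect on ranking.** Take d = 0.50, so 30 delayed procedures, and two unrelated events with e = 0.20 and e = 0.40. They are present in 30 × 0.20 = 6 and 30 × 0.40 = 12 delayed procedures. With an equal share a, the second is credited twice as often, purely because it is more common. If reviewers never credited an unrelated event (a = 0), the problem would disappear, but these outcomes contain nothing against which to check that.

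**Step 4. What coding in all procedures would allow.** Compare the risk of delay with and without the event. The standard error is √[d(1−d)/n₁ + d(1−d)/n₀].

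- d = 0.50, e = 0.40: n₁ = 24, n₀ = 36. SE = √(0.25/24 + 0.25/36) = 0.132. The 95% half-width is 1.96 × 0.132 = about 26 percentage points.
- d = 0.30, e = 0.20: n₁ = 12, n₀ = 48. SE = √(0.21/12 + 0.21/48) = 0.148. The half-width is about 29 points.

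Power was also computed at two-sided alpha 0.05 (assumed), with 30% to 50% of procedures delayed and the event in 20% of undelayed procedures. It is about 0.37–0.39 if the event is in 40% of delayed procedures, 0.65–0.69 if in 50%, and 0.86–0.91 if in 60%. The comparison can be made but is imprecise, which suits estimation rather than testing.

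**The case against.** The strongest reply is that the study does hold the needed data. All eligible procedures are recorded and all are rated for skills. Event occurrence is collected with no stated limit to delayed cases, and the second objective in Section III correlates skills with case duration without conditioning on delay. An analysis plan could add the event comparison, and its absence from a protocol is not in itself a fault. This stands, and it rules out inferring that the study has no comparison at all. Whether Appendix 3 logs events regardless of delay cannot be checked.

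It does not settle the matter, because the outcome section still defines what is to be reported. If analysts code to that definition, an analysis plan written later cannot recover uncoded events from deleted recordings.

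Other parts of the reply also stand:

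- A reader might infer that "correlation of time delay to its root cause" has no variation. That is true only of delay yes/no. Minutes of delay and category of cause can both vary among delays.
- A reader might see a conflict with the word prospectively. Prospective recording followed by later review is compatible with it.
- A reader might infer that rare but harmful events would be missed. They would be counted each time they were credited with a delay, and would merely rank low.
- The outcome asks for attribution and not mere presence, so the a = 1 illustration is an upper extreme.

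**Conclusion.** The concern holds for the three event-related secondary outcomes as worded. They are conditional on a delay attributed in hindsight, and on their own they cannot separate events associated with delay from common background events. In the illustration, an event with a true odds ratio of 1 appears only alongside delays, whatever share of it reviewers credit, provided that share is above zero. The zero cell follows from the definition, while the size of the distortion depends on delay rates, event rates and reviewer behaviour, none of which the protocol gives.

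The primary objective, the incidence and categorization of delays, is not affected, nor is the correlation of skills with case duration. The documents do not show that undelayed procedures are left out of the data. A comparison across all procedures would show association and not cause, and would be imprecise with about 60 procedures. The outcome definition should be changed because the change is cheap and the coding cannot wait until after the recordings are deleted.

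**What to change.** In *Primary Outcome Measure*, replace the event outcome with: *incidence of each pre-listed event per procedure, coded in all recorded procedures without reference to whether a delay followed*. Then:

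1. State that this coding is completed for each procedure before its recording is deleted at 30 days. Where practical, events should be coded by raters who do not know the delay status.
2. Report delay (yes/no and minutes) or case duration with versus without each event, as a risk or mean difference with a 95% confidence interval. Describe the results as exploratory association, given about 60 procedures and several events.
3. Define the outcome on the impact of skills over these same events, coded in all procedures.
4. Keep the retrospective root-cause attribution as a descriptive outcome, labelled as reviewer judgement.

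The cost is a wording change, a coding instruction and some extra coding of events without consequence. No further recording is needed. If Appendix 3 already requires events to be logged in every procedure, only the outcome wording and the reporting need to change.

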#### *Statistical Analysis*

This observational study represents a pilot study. Therefore, an *a priori* analysis of statistical power and sample size cannot be performed (see also chapter *sample size*). Descriptive statistical analysis of defined events and outcomes will be performed. Correlation statistic will be performed to evaluate the team's conscious awareness of incidents and adverse events. Logistic regression analysis will be performed to identify influencing non-technical and team performance factors. A biostatistician will be involved in the statistical analysis of the results.

#### **VI. Ethics**

Ethics approval for this study will be obtained from the Research and Ethics Boards from the participating hospital and the University of Toronto.

#### **VII. Relevance**

OR delays due to inefficiency can result from a chain of intraoperative events including technical factors (ie. equipment failure or case complexity) and from non-technical human factors (ie. communication errors or lack of coordinated teamwork within and between OR teams). Objective measures of intraoperative OR delays and identification of their causes can lead to the development of a standardized framework that could be generalized to any surgical discipline to improve OR efficiency. Anticipated outcomes include: reduced cancellation of cases, increased OR utilization, reduced time delays, increased number of completed cases, improved patient flow within peri-operative department, and

improvement in non-technical skills of surgeons, anesthetists, nursing, and administrative team when facing challenges in time delays.

